7.4.2 RELATIONSHIP TO STUDY AGENT

All AEs will have their relationship to study agent or study participation assessed.

Evaluation of relatedness will consider etiologies such as natural history of the underlying disease, concurrent illness, concomitant therapy, study-related procedures, accidents, and other external factors.

The clinician’s assessment of an AE’s relationship to study agent is part of the documentation process, but it is not a factor in determining what is or is not reported in the study. If there is any doubt as to whether a clinical observation is an AE, the event should be reported. All AEs must have their relationship to study agent assessed. In a clinical trial, the study product must always be suspect. To help assess, the following guidelines are used.

- **Related** – The AE is known to occur with the study agent, there is a reasonable possibility that the study agent caused the AE, or there is a temporal relationship between the study agent and event. Reasonable possibility means that there is evidence to suggest a causal relationship between the study agent and the AE.
- **Not Related** – There is not a reasonable possibility that the administration of the study agent caused the event, there is no temporal relationship between the study agent and event onset, or an alternate etiology has been established.

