2.3 POTENTIAL RISKS AND BENEFITS

2.3.1 KNOWN POTENTIAL RISKS & RISK ANALYSIS

Potential risk of the mask includes swelling, itching, pain, dermatitis, erythema, or hypersensitivity.

Potential risk of the cosmetic treatments include swelling, itching, pain, dermatitis, erythema, infection, bleeding or scarring.

To mitigate the risk, patients will be educated on how to properly care for their skin post-procedure and all patients in the ablative arm will be receiving oral antibiotics and antivirals for infection prevention.

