5.1.4 PREPARATION

The subject's face will be cleansed with a cleansing cloth to remove all topicals such as make-up, sunscreen, and moisturizers. A topical numbing cream will be applied for 30 minutes and then removed before the subject's face will be cleansed with alcohol immediately prior to the laser procedure.

The product will be removed from original packaging, cut in half with a sterile scissor, and placed on the subject's assigned side within 5 minutes of the end of the procedure.

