7.7 STUDY HALTING RULES

Administration of the study agent will be halted when two SAEs determined to be related are reported. The primary investigator will notify the IRB and FDA and investigators immediately when the second

serious adverse event is reported, and enrollment screens will stop accepting new study participants. The study sponsor will inform the FDA of the temporary halt and the disposition of the study.

Additionally, enrollment and treatment into the study will be temporarily halted if the Sponsor receives a SAE for a vascular embolic event that lead to skin necrosis, vision loss, stroke, pulmonary or cardiac complications or death and is determined by the Investigator to be directly or possibly related to the study device or injection procedure. The SAE will be investigated by the Sponsor. If the Sponsor's investigation concludes:

- The SAE was unanticipated, directly related to the study product or device injection procedure, and presents an unreasonable risk to study subjects, the study will be terminated. The IRB and FDA will also be notified if the study is prematurely terminated due to safety concerns.
- If the SAE does not meet the above criteria, then enrollment in the study will continue.

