8.3 SAFETY ANALYSIS

Safety analysis will be descriptive only.

The number and percentage of subjects reporting each post-treatment symptom will be presented in total and by maximum severity.

A summary of all AEs will be provided, which will include:

- number of subjects with at least one AE and number of events (in total as well as serious AEs)
- number of subjects with at least one related AE and number of events (in total as well as serious AEs)
- number of subjects with at least one mild, moderate, and severe AE and number of events (in total as well as serious AEs)
- number of subjects with at least one unrelated AE and number of events (in total as well as serious AEs)
- number of subjects who did not have an AE

The number of subjects with AEs related to the study product as well as the number of events will be summarized, and action taken for related AEs will also be summarized. Serious AEs will be listed.

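### The Related and Not Related definitions in 7.4.2 overlap with no precedence rule, so the related-AE counts in 8.3 cannot separate mask effects from procedure effects

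*Combined protocol and SAP*

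**What the plan says.** Section 7.4.2 offers two categories. An AE is Related if it is known to occur with the study agent, or if "there is a reasonable possibility that the study agent caused the AE, or there is a temporal relationship between the study agent and event". It is Not Related if there is no reasonable possibility of causation, or if "there is no temporal relationship between the study agent and event onset, or an alternate etiology has been established". The same section tells the assessor to weigh other causes, among them "concurrent illness, concomitant therapy, study-related procedures, accidents, and other external factors", and adds a default stance: "In a clinical trial, the study product must always be suspect".

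The rest of the plan supplies the context:

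- **Timing (5.1.4).** The half mask goes on the "assigned side within 5 minutes of the end of the procedure". Masks are then worn at home each day until healing.
- **Risks (2.3.1).** "Potential risk of the mask includes swelling, itching, pain, dermatitis, erythema, or hypersensitivity". The procedure list repeats the first five of these and adds infection, bleeding and scarring.
- **Recording (7.5, item g).** There is one yes/no causality item, covering the study product or an injection procedure. Item b records the affected area.
- **Analysis (8.3).** The summary includes the "number of subjects with at least one related AE and number of events". Nothing is broken down by side of the face.
- **Halting (7.7).** "Administration of the study agent will be halted when two SAEs determined to be related are reported".
- **Endpoint (3.2.2).** Safety is measured by the between-side difference in the number of AEs.
- **Follow-up (6.3.3).** The AE instruction names only the side assigned to the mask.

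**The concern.** Relatedness categories are useful only if they sort events by cause. Here the two candidate causes act on the same skin minutes apart and share most of their listed reactions, so neither timing nor the type of reaction separates them well. If the two definitions can both be true of one event, the related-AE table reflects the assessor's choice of definition as much as any property of the mask.

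Mask safety is the first-listed secondary objective, and the related-AE counts are the only summary in 8.3 that is specific to the mask. The word related also feeds the halting rule, so an unclear label carries over into 7.7.

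**Working it through.** The plan states no figure on this point, so there is none to reproduce. The check has three parts.

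**1. Logic of the definitions.** Take swelling that appears on both cheeks within the hour after ablative laser.

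| Limb in 7.4.2 | Met? | Points to |
|---|---|---|
| Known to occur with the mask | Yes; swelling is on the mask list in 2.3.1 | Related |
| Temporal relationship to the mask | Yes; mask applied within 5 minutes of the procedure | Related |
| Alternate etiology established | Can be; the laser was applied to both cheeks | Not Related |

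Each definition is a list joined by 'or', so one limb is enough. The event meets both definitions. The instruction to consider study-related procedures lets the assessor choose Not Related. The instruction always to suspect the product leans the other way. No sentence ranks the two.

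**2. Overlap of the risk lists in 2.3.1.**

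- Mask: swelling, itching, pain, dermatitis, erythema, hypersensitivity = 6 terms.
- Procedures: swelling, itching, pain, dermatitis, erythema, infection, bleeding, scarring = 8 terms.
- Shared: swelling, itching, pain, dermatitis, erythema = 5 terms, that is 5 of 6 mask terms and 5 of 8 procedure terms.

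Only hypersensitivity is specific to the mask. Infection, bleeding and scarring are specific to the procedures.

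**3. What a timing-only label would count.** The documents give no AE rates, so this is an illustration on assumed values. Let q be the probability that a subject has a procedure AE on the masked side, and m an independent probability of a mask-caused AE. With N = 15:

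- Expected subjects with a mask-side AE labelled Related on timing alone = 15 × [1 − (1 − q)(1 − m)].
- The part that is excess due to the mask = 15 × m × (1 − q).

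| q (assumed) | Labelled Related, m = 0 | Labelled Related, m = 0.1 | Mask excess, m = 0.1 | Share |
|---|---|---|---|---|
| 0.1 | 1.5 | 2.85 | 1.35 | 47% |
| 0.3 | 4.5 | 5.55 | 1.05 | 19% |
| 0.5 | 7.5 | 8.25 | 0.75 | 9% |
| 0.8 | 12.0 | 12.3 | 0.30 | 2% |

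With no mask effect the count runs from 1.5 to 12 of 15 subjects, driven wholly by q, while the expected between-side difference is 0. This is the behaviour if assessors use the timing limb. If they use the alternate-etiology limb the count could be near zero, and then events the mask did contribute to may be lost.

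**Records.** Item g in 7.5 cannot show which limb was used or whether the laser or RF procedure was thought to be a cause. The injection procedure it names is not part of this trial. The reporting list in 7.6.1 also puts product and procedure into one relatedness item.

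**The case against.** The strongest reply has four parts.

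- **Events are not forced to Related.** A reader might infer from the timing limb alone that every early reaction must be charged to the mask. The documents do not support that. Section 7.4.2 presents the definitions as guidelines, requires study-related procedures to be considered, and allows Not Related when another cause is established. This stands. The defect is assessor-dependent classification.
- **The safety objective does not rest on relatedness.** A reader might also infer that the mask-safety objective cannot be answered. Its declared endpoint is the between-side AE difference, which uses the subject's own unmasked cheek as control and needs no causality call. This stands in principle. The supporting text is incomplete, though: 6.3.3 names only mask-side AEs and 8.3 has no by-side table. Section 7.5 and the schedule of events do ask for AEs at each visit without limiting the side, and item b records location, so both-side data may well be collected. The plan should say so in one place.
- **Broad attribution is a deliberate, cautious choice, and 8.3 is descriptive.** That is fair as a safety stance. It does not explain how an event that meets both definitions should be labelled.
- **The halting concern is speculative.** Section 7.7 counts SAEs judged to be related, and a medical monitor reviews all AEs. The documents do not show that procedure complications would trigger a halt. What remains is that the word has no single meaning in the plan.

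**Conclusion.** The point holds in a limited form. The two relatedness categories overlap with no precedence, and the aesthetic procedure has no causality field of its own. The related-AE counts in 8.3 therefore cannot separate mask effects from procedure effects. The firm figures are the 5-of-6 overlap in listed risks and the 5-minute interval. The counts in the illustration rest on assumed AE rates and on assessors using the timing limb. They show direction and do not predict.

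One might be tempted to say that all 15 subjects could be labelled mask-related. That figure is only the sample size. It would require every subject to have an AE and every assessor to set aside the alternate-etiology limb, and nothing in the documents suggests either.

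The primary temperature endpoint is not affected. The correction is worth making because mask safety is a stated objective and the change is mostly wording.

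**What to change.** 1. **7.4.2.** Make Related and Not Related mutually exclusive. State that timing alone is not sufficient when the aesthetic procedure is an equally timed candidate cause.
2. **7.5, item g.** Replace it with two fields, causality to the mask and causality to the aesthetic procedure, and allow both to be yes. Remove the reference to an injection procedure, and align the reporting list in 7.6.1.
3. **6.3.3.** Record AEs by side, for both cheeks, at every visit.
4. **8.3.** Tabulate the two causality fields separately, and add a table of AEs by side to match the endpoint in 3.2.2.
5. **Unmasked cheek.** Give its findings to the assessor as information, not as an automatic attribution rule. A hypersensitivity reaction to the mask may be bilateral, and a side-based rule would assign it to the procedure.
6. **7.7.** The sponsor must reconcile 7.4.2 and 7.5 with 7.7 so that related has one stated meaning there, because rewording 7.4.2 could otherwise change which SAEs are counted. No halting rule is proposed here.

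The cost is wording in these sections, one extra CRF field, one added table, and two causality judgements per event instead of one.

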7.4.3 EXPECTEDNESS

The primary investigator will be responsible for determining whether an AE is expected or unexpected. An AE will be considered unexpected if the nature, severity, or frequency of the event is not consistent with the risk information previously described for the study agent.

7.5 RECORDING INSTRUCTIONS

Investigators, or other study site personnel, shall record all AEs including:

- a) Event term (recorded in standard medical terminology and avoiding abbreviations)
- b) Affected area
- c) Start date (first day with symptoms)
- d) Stop date (last day with symptoms)
- e) Intensity (mild, moderate, or severe)
- f) Seriousness (serious or not serious)
- g) Causal relationship to study product or study product injection procedure (yes or no)
- h) Action taken (none, medication treatment, non-pharmacological treatment, or other procedures/tests, subject withdrawn)
- i) Outcome of the AE (ongoing, recovered, recovered with sequelae, death, chronic/ stable, not recovered at the end of the study)

All AEs, non-serious as well as serious, are to be reported as an AE. The PI will record all reportable events with start dates occurring any time after informed consent is obtained until 7 (for non---serious AEs) or 14 days (for SAEs) after the last study intervention. At each study visit, the investigator will inquire about the occurrence of AE/SAEs since the last visit. Events will be followed for outcome information until resolution or stabilization.

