**A Split-Face Multi-Arm Randomized Clinical Trial
Showing the Efficacy & Safety of a Topical Mask After
Aesthetic Treatments**

[name]

A Split-Face Multi-Arm Randomized Clinical Trial Showing the Efficacy & Safety of a Topical Mask After Aesthetic Treatments.

Principal Investigator: [name]

[name]

[name]

[contact]

[contact]

Email Address: [contact]

Study Coordinator:

[name]

[name]

[name]

[contact]

[contact]

Email Addresses: [contact]

Sponsor: Velez

STATEMENT OF COMPLIANCE

The trial will be conducted in accordance with the ICH E6 and the Code of Federal Regulations on the Protection of Human Subjects (45 CFR Part 46). The Principal Investigator will assure that no deviation from, or changes to the protocol will take place without prior agreement from the sponsor and documented approval from the Institutional Review Board (IRB), except where necessary to eliminate an immediate hazard(s) to the trial participants. All personnel involved in the conduct of this study have completed Human Subjects Protection Training.

I agree to ensure that all staff members involved in the conduct of this study are informed about their obligations in meeting the above commitments.

[name]

PROTOCOL SUMMARY

Title: A Split-Face Multi-Arm Randomized Clinical Trial Showing the Efficacy & Safety of a Topical Mask After Aesthetic Treatments.

Précis: Subjects undergoing aesthetic facial treatments with either a fractionated non-ablative 1927nm Thulium laser (Sciton Moxi), ablative Erbium:Yag 2940nm (Sciton Contour), or Microneedling with Radiofrequency (Cutera Secret) will apply a face mask immediately after the procedure randomly on either their left or right side of their face with normal post-care on the other side of the face. Thirty minutes after the mask is applied to one side both regular photography and thermal photography will be done. In addition, subjects will fill out questionnaires and will be assessed by blinded evaluators for efficacy and potential side effects. Patients will wear the masks at home for at least two hours a day and return daily for photographs until deemed healed by the primary investigator (3-7 days). Patients will also fill out daily questionnaires.

Mask, Pain, Temperature, Post-Laser Care

Keywords:

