Objectives: Primary Objective: To assess the efficacy of a facial mask in decreasing facial skin temperature after three different aesthetic treatments

Important Secondary Objectives:

1. To determine the safety and incidence of adverse events when using a Velez face mask after 3 different aesthetic treatments
2. To assess the change in the level of pain when using a Velez face mask after aesthetic treatments
3. To assess patient satisfaction with use of a Velez face mask after aesthetic treatments
4. To assess erythema when using a Velez face mask after aesthetic treatments
5. To assess healing time when using a Velez face mask

Primary

Endpoints:

Primary Endpoint:

The difference between the temperature on the mid-cheek (point inferior to the lateral limbus).

Important Secondary Endpoints:

1. The difference in the number of adverse events between the two sides of the face
2. The difference in pain scores on each side of their face as rated by subjects
3. The difference in patient satisfaction scores when rating the procedure on the left and right side of their face
4. The difference in erythema on the left and right side of subject's faces as graded by blinded evaluators doing live assessments 30 minutes after the procedure
5. The difference in healing time on the left and right side of subject's faces as graded by blinded evaluators looking at daily photographs

Population: Healthy adults aged 21 and over living in Palm Beach County, Florida.

Sample Size: 15

Study Sites: [name] &
[name]

Duration: 7 days

Study Agent: Velez Intense Hydration Mask

SCHEMATIC OF STUDY DESIGN

- Total n=15
- Screen potential subjects by inclusion and exclusion criteria

Day 0 Randomization

- Obtain informed consent, randomize into one of the following two groups
- Treatment Group 1 Right Side Velez Intense Hydration Mask
- Treatment Group 2 Left Side Velez Intense Hydration Mask

Day 0 Baseline assessments/ Study Intervention

- Baseline Assessments:
 - Pre-procedure pictures taken with Canfield's imaging system (Front, Right and Left Views)
- Study Intervention:
 - 1st Arm (n=5)

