5.1.7 DURATION OF THERAPY

The subject will remain in the office for 30 minutes with the Velez face mask applied immediately after their laser treatment.

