6.2.2 ENROLLMENT/BASELINE

Enrollment/Baseline Visit (Visit 1, Day 0)

- Review in depth the study design with subjects and obtain informed consent of potential participants verified by signature
- Perform examination and verbally review subject's medications and medical history to determine eligibility based on inclusion/exclusion criteria.
- Verify all inclusion/exclusion criteria.
- Obtain demographic information
- Randomization
- Perform either a Sciton Moxi, Sciton Erbium, or Secret RF treatments to subject's face, and then apply a half mask on one side of the face according to randomized groups.
- Record adverse events as reported by participant or observed by investigator or blind evaluator.
- Perform protocol adherence check by study coordinator
- Collect post-procedure subject questionnaires
- Take post-procedure photos

- After photographs and blind evaluation both side of the face will be treated with the normal post-procedure care such as Vaseline for laser resurfacing and a Hydrating serum for Moxi and Microneedling. Additional masks will be given to patients to wear for 2 hours at home each day until deemed healed by the primary investigator.

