6.3.3 FOLLOW -UP

Follow Up Visits (Visit 2-8, Day 1-7)

- Record adverse events as reported by participant on side assigned the mask
- Photograph with both thermal camera and Canfield standardized photography
- Primary investigator to advise each day if they need to return the next day or are done with the study and completely healed

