6.3.7 SCHEDULE OF EVENTS TABLE

Procedures	Screening	Enrollment/Baseline Visit 1, Day 0	Day 1	, Day 2-	, Day 3-	, Day 4-	, Day 5-	, Day 6-	, Day 7-
Informed consent & Randomization		X							
Demographics & Medical History		X							
Aesthetic Treatment		X							
Subject Questionnaire	X	X	X	X	X	+/-X	+/-X	+/-X	+/-X
Exam for Adverse Effects		X	x	x	x	+/- x	+/- x	+/- x	+/- x
Exam by blinded Evaluator		X							
Intervention with Face Mask		X	x	x	x	+/- x	+/- x	+/- x	+/- x
Photos		X	x	x	x	+/-x	+/-x	+/-x	+/-x

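### The adverse-event recording window runs past the last scheduled contact with completers, and the date it starts from is not defined

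*Combined protocol and SAP*

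**What the plan says.** Section 7.5 (Recording Instructions) has the principal investigator record events starting at any time from consent "until 7 (for non---serious AEs) or 14 days (for SAEs) after the last study intervention". In the same paragraph, the investigator asks about events at each study visit.

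The visits are short. The Protocol Summary gives "Duration: 7 days", and its précis has subjects "return daily for photographs until deemed healed by the primary investigator (3-7 days"). Section 6.3.3 lists "Follow Up Visits (Visit 2-8, Day 1-7") and sets the exit rule: "Primary investigator to advise each day if they need to return the next day or are done with the study and completely healed". The schedule of events (6.3.7) has no column after Day 7.

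The mask continues over the same days. Section 6.2.2 states: "Additional masks will be given to patients to wear for 2 hours at home each day until deemed healed by the primary investigator". The schedule table carries a row named "Intervention with Face Mask", marked on Days 0 to 3 and conditionally on Days 4 to 7. Section 3.1, however, places the study intervention on Day 0, and Section 5.1.7 on duration of therapy describes only the office session: "The subject will remain in the office for 30 minutes with the Velez face mask applied".

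**The concern.** The mask and the visits end on the same judgement, that the subject has healed. A window counted from the last mask therefore opens at about the time planned observation closes. Staff also cannot tell from the text which day starts the count, so an event on Day 10, for example, may or may not be reportable.

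Safety is the first secondary objective, and the difference in adverse events between the two sides is the first secondary endpoint. Section 8.3 will report event counts and also the number of subjects with no event. A completer who is never asked during the stated window would be reported as event-free for it. The halting rule in Section 7.7 needs two related serious events to be known. With 5 subjects per arm, one missed event is 1/5 = 20% of an arm.

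**Working it through.** The plan gives no derived figure to reproduce, because the window is a rule. The check is date arithmetic.

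**Inputs**
- Window length W: 7 days (non-serious) or 14 days (serious), from Section 7.5.
- Last scheduled visit on Day k, with k from 3 to 7, from the précis, Section 6.3.3 and the schedule table.
- Last study intervention on Day L, which the protocol does not define. Three values are tried:
  - L = k: the last mask is worn on the day of the last visit.
  - L = k − 1: the last mask is worn the day before the last visit.
  - L = 0: only the Day 0 session counts.

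**Formulas**
- Window end = L + W.
- Days without scheduled contact = max(0, L + W − k).

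**One subject, last visit on Day 5**
- L = 5: the windows end on Day 5 + 7 = 12 and Day 5 + 14 = 19. Uncovered days are 12 − 5 = 7 and 19 − 5 = 14.
- L = 4: the windows end on Days 11 and 18. Uncovered days are 6 and 13.
- L = 0: the windows end on Days 7 and 14. Uncovered days are 7 − 5 = 2 and 14 − 5 = 9.

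**All k from 3 to 7**

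| Reading | Non-serious window ends | Days uncovered | Serious window ends | Days uncovered |
|---|---|---|---|---|
| Last mask, day of last visit | Day 10-14 | 7 of 7 | Day 17-21 | 14 of 14 |
| Last mask, day before last visit | Day 9-13 | 6 of 7 | Day 16-20 | 13 of 14 |
| Day 0 only | Day 7 | 0-4 of 7 | Day 14 | 7-11 of 14 |

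On the Day 0 reading, the non-serious window is fully covered only for a subject followed to Day 7. The serious window is not fully covered on any row.

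**Does another section fill the gap for completers?**
- Section 6.3.6 records unscheduled visits but plans none.
- Section 7.6.1 names visits, questionnaire review and subjects presenting for medical care. The questionnaires also end by Day 7.
- Sections 7.5 and 7.6.1 follow events to resolution or stabilization, which applies to events already known and does not detect new ones.
- Section 4.4.2 provides contact by the investigator, but only with subjects who withdrew or were terminated.

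None of these schedules a contact for a completer after discharge.

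**The case against.** The strongest reply is that Section 7.5 is a recording rule and does not promise active enquiry on the last day of the window. Passive routes stay open, and subjects come from the practice's own patients, so returning with a problem is plausible. That stands. A reader might infer that all contact ends at discharge and that the window is never observed. The documents support only that no contact is scheduled. The part of the period from consent to the last visit is observed.

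A reader might also infer that all 7 and all 14 days are uncovered in every subject. That is the upper end of the range. It assumes that the last mask starts the clock and is worn on the day of the last visit. Section 3.1 supports a Day 0 reading with much smaller gaps.

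A third tempting inference is that late infection or scarring would distort the comparison between sides. Section 2.3.1 lists those two only for the cosmetic procedures, which both sides receive. Dermatitis and hypersensitivity are among the risks it lists for the mask. The documents do not show that missed procedure-related events would favour one side.

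Finally, discharge requires the subject to be judged healed, so problems evident at the last visit would be recorded and followed, and the safety analysis is descriptive. Both points limit the consequence. Neither removes the mismatch between window and schedule.

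**Conclusion.** The point holds as a mismatch between the stated recording window and the schedule, together with an undefined starting date. Across the readings, 0-7 of the 7 days for non-serious events and 7-14 of the 14 days for serious events have no scheduled contact. The schedule table's own label favours the last daily mask, which puts the gap at 6-7 and 13-14 days. The shortfall for serious events does not depend on the choice of reading.

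What would be lost is new onsets after discharge that never reach the site. They would be absent from the descriptive adverse-event summary and from the count of serious events. The documents give no rate for such events, so the number missed cannot be estimated. The primary temperature endpoint is unaffected. The result assumes that each completer's last visit falls between Day 3 and Day 7 and that the mask is worn no later than that visit.

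**What to change.** Reconcile the Protocol Summary, Sections 3.1, 5.1.7, 6.3.3 and 7.5 and the schedule table by defining the last study intervention once. The schedule table supports using the last home mask application. Then add a brief remote contact at the end of each stated window, 7 and 14 days after that date. Each contact should ask about events on both sides of the face, because Section 6.3.3 currently refers only to events on the masked side and the endpoint compares the two.

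If no contact is added, restate the window as ending at the last scheduled visit, and report anything later as spontaneous only, so that the summary does not imply enquiry that did not take place.

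Cost of the first option: at most 15 subjects × 2 = 30 short contacts, with no added visits or procedures. Participation would extend to about Day 7 + 14 = Day 21 at the latest, so the stated duration and schedule must change through an IRB-approved amendment. The text, email and phone channels in Section 4.3 are set up for visit reminders, so a short set of adverse-event questions would have to be written for them. The second option needs only an amendment of the text, but it gives up the later part of the window.
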